NCT04834817 Effect of Combined Red and Near Infrared Light-emitting Diode (LED) Therapy on Tissue Regeneration Post Laser Treatment (Document date: 11/29/2023)

[figure not shown]
STUDY PROTOCOL

Background & Purpose of the Research

The objective of this study is to evaluate the effect of a combination of near infrared (830 nm) red (633 nm) and blue (465nm) light-emitting diode (LED) therapy on wound healing after application of low density ablative fractional laser to bilateral inner biceps, close to the axilla. Our hypothesis is that the LED therapy will result in less post treatment pain and in a faster healing time after ablative fractional laser application.

Literature reveals that light-emitting diodes (LED) promote healing of skin wounds by decreasing inflammation, increasing fibroblast proliferation, stimulating angiogenesis, formation of granulation tissue, and increasing collagen synthesis.1 LED treatment is of interest to the medical community in large part for its safety profile – at 6.5 milliwatts, it emits energy far less than that of a household flashlight. To further determine the extent to which LED promotes healing and to evaluate the relative speed at which it does so compared to other conservative management, this study sets out to assess wound healing with LED treatment after application of fractional ablative laser to the bilateral inner biceps, close to the underarm. Ablative fractional laser treatment results in well-healed regeneration of the superficial layers of the skin, thus an ablative fractional laser with the following parameters will be used to induce a two-inch by two-inch, superficial wound on each ventral bicep: 650 micrometers at 150 J and 5.5% density, similar to parameters used to treat scars. After laser application, we will evaluate the effect of a combination of near infrared (830 nm) red (633 nm) and blue (465nm) light-emitting diode (LED) therapy on wound healing post laser treatment. Product under investigation: BioPhotas Celluma LED device Technical parameters Red: 640nm+/-25nm NIR: 880nm+/-50nm Blue 465nm Irradiance 6.5 mW/cm2 Fluence 11.7J/cm2

Literature reveals that light-emitting diodes (LED) promotes healing of skin wounds by decreasing inflammation, increasing fibroblast proliferation, stimulating angiogenesis, formation of granulation tissue, and increasing collagen synthesis. One proposed mechanism for these changes called the Karu Model is shown below (Figure 1):

Source: Huang YY, et al. 2009.

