Many studies have demonstrated these effects on wound healing in vitro, as below, where "LLLT" refers to low-level light therapy. See Figures 2 & 3 below.

[figure not shown]
[figure not shown]

Fig. 3 LLLT increases *in vitro* wound healing in A549, PtK2, and U2OS using wavelengths 806 and 901 nm. (a and b) Cells were treated and evaluated as in (Fig. 2), but treated with LLLT 806 or 901 nm and wound healing was measured after 24 h. The green area marks the wound, bar, 100 μ m. Data represent the mean \pm SEM of at least three separate experiments with N=12; ****p<0.0001, *p<0.05 compared with control or for the indicated comparison.

Spitler and Berns: Comparison of laser and diode sources for acceleration of in vitro wound healing...

Nasa has demonstrated reproducible results here. See Figure 4, 6, and 7.

[figure not shown]

FIG. 4. LED response at 4 J/cm², 50 mW/cm² using individual wavelengths of 670, 728, and 880 nm (percentage change from control versus number of hours after LED treatment).

[figure not shown]

FIG. 6. HaCAT epithelial cell collagen synthesis at 8 J/cm², 50 mW/cm², 670 nm. Shown in 24-h ³H proline incorporation.

[figure not shown]

FIG. 7. Change in wound size in rat ischemic wound model versus time (days).

[figure not shown]
There is also evidence that LED treatment post-sternotomy leads to a decrease in bleeding and dehiscence, while providing an analgesic effect.

Visible LED light treatment at various wavelengths have been shown to not only increase growth in multiple cell lines but also to accelerate wound healing in human studies for skin grafts, chronic leg ulcers, and post-CO2 laser treatment.

Further study on the mechanism by which LLLT induces these changes suggests that LED causes changes in mitochondrial complexes I, II, III, IV, succinate dehydrogenase, and cytochrome C (part of complex IV) ultimately leading to increased nitric oxide (NO) and thus increased wound healing.

Given these past results, we now want to confirm response in human subjects.

Spitler and Berns: Comparison of laser and diode sources for acceleration of in vitro wound healing...

The primary endpoint of this study is time in days to complete healing of the treatment sites. Clinical grading shall be by blinded assessment, using recognized assessment techniques. A secondary outcome measure will be post-treatment pain on a 10-point scale.

Relevant references/articles to support the rationale for the research:

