Appropriate eye protection in the form of dedicated laser goggles will be provided to the patient and all other individuals in the treatment room. Ablative fractional laser treatment test area will be (5.5% density/700um) delivered to both inner biceps, close to the underarm to an approximately 3 x 3 cm square area. Subjects will evaluate pain and discomfort immediately after the treatment using an 11-point Visual analogue scale. Clinical digital photography of test and control site post induction will be recorded. Immediately after photography the test area will be irradiated with the Biophotas Celluma for 30 minutes. The Celluma light panel will be disinfected prior to every use over open wound. The Control side will be untreated. The Celluma POD device will not be used over known cancer tumor or metastasis.

30 minutes after treatment with the Biophotas Celluma subjects will evaluate pain and discomfort for test and control sites using an 11-point Visual analogue scale.

Days 1-27 – treatment with Celluma

Test site will receive a 30-minute treatment of Celluma, 3 treatments per week for 4 weeks, with the first treatment being day 0 immediately after ablative fractional laser treatment test area. Day 1, 3, 6 subjects will record daily site symptoms including pain and discomfort and complete a treatment log in a patient diary.

Days 2*, 4*, 6*, 9, 13, 20, and 27 – Assessments

* Scheduled follow-up visits may be adjusted 1-2 days based on clinic or patient availability.

Clinical digital photography of test and control site will be recorded. Investigator assessment of treatment response using visual analogue scales to include Time to heal, Percentage healing, edema, erythema, swelling and crusting.

Subject assessment of treatment response using a grading of response.

Day 34 – Assessments Clinical digital photography of test and control site will be recorded. Investigator assessment of treatment response using visual analogue scales to include Time to heal, Percentage healing, edema, erythema, swelling and crusting.

Subject assessment of treatment response using a grading of response.

Day 55 – Final follow up

Clinical digital photography of test and control site will be recorded.

Investigator assessment of treatment response using visual analogue scales to include Time to heal, Percentage healing, edema, erythema, swelling, crusting, discoloration, and scarring

Subject assessment of treatment response using a grading of response.

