If either or both skin wounds have not completely healed by this time, an additional follow-up visit will be scheduled at day 62 (one week after original final follow-up visit).

Study Narrative and Baseline Day 0

- 1. After completing informed consent and photography release forms subjects will be enrolled into the study.
- 2. Subjects will be randomized to which arm denotes the test or control side.
- 3. The clinical investigator will assess baseline characteristics including assessment of Fitzpatrick skin type, ethnicity, demographics and general medical history and status, and concomitant medications.
- 4. Subjects will be instructed on the use of the Biophotas Celluma LED device and observed switching the device ON/OFF, positioning the device and after treatment care of the device.
- 5. Clinical digital photography of treatment site will be recorded immediately prior to treatment
- 6. Ablative fractional laser treatment test area (5.5% density/700um) will be delivered to both inner biceps, close to the underarm an approximately 3×3 cm sq area.
- 7. Immediately after the test area administration, subjects will evaluate pain and discomfort using an 11- point Visual analogue scale.
- 8. Clinical digital photography of test and control site post induction will be recorded.
- 9. Immediately after photography the test wound will be irradiated with the Biophotas Celluma for 30 minutes. The Control side will be untreated. Subjects will be observed self-administrating the treatment.
- 10. 30 minutes after treatment with the Biophotas Celluma subjects will evaluate pain and discomfort for test and control sites using an 11-point Visual analogue scale.
- 11. Subjects will be instructed to treat the test site daily for 28 days and to complete their treatment log and diaries daily. Subjects will be given contact details for any adverse incidents or questions they may have.
- 12. Subjects will be given a date and time to return to the clinic for assessment.

Days 1-27

- 1. Subjects will complete their diaries and treatment log daily.
- 2. Daily, immediately before and 30 minutes after each Biophotas Celluma treatment the subject will record pain and discomfort.
- 3. From Day 2-27 subjects will record itching immediately before and 30 minutes after each Biophotas Celluma treatment.

Days 2*, 4*, 6*, 9, 13, 20 and 27 - Assessments

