Clinical assessment shall be performed by independent and blinded assessors, based on visual examination and clinical photography of the test and control areas at baseline (before the first session), and at each assessment point.

Swelling shall be graded at each assessment on a 11-point scale as follows:

- i. No Swelling evident
- 0
- 1
- ii. Mild Swelling
- 2
- 3
- 4
- iii. Moderate Swelling

- 5
- 6
- 7

iv. Severe Swelling

- 8
- 9
- 10

Crusting

Clinical assessment shall be performed by independent and blinded assessors, based on visual examination and clinical photography of the test and control areas at baseline (before the first session), and at each assessment point.

Crusting shall be graded at each assessment on a 11-point visual analogue scale as follows:

- i. No crusting evident
- 0
- 1

ii. Mild Crusting

- 2
- 3
- 4

iii. Moderate Crusting

- 5
- 6
- 7

iv. Severe Crusting

- 8
- 9
- 10

Subject assessment

Pain

Pain shall be assessed using an 11-point Visual Analogue Scale (VAS) (0-10-point scale). The Scale will be used at the following timepoints.

- i. Immediately after the test area performance
- ii. 30 minutes after the first treatment session of Biophotas Celluma.
- iii. Daily, immediately before and 30 minutes after each Biophotas Celluma treatment.

Discomfort

Discomfort shall be assessed using an 11-point Visual Analogue Scale (VAS) (0-10-point scale). The Scale will be used at the following timepoints.

- i. Immediately after the test area performance
- ii. 30 minutes after the first treatment session of Biophotas Celluma
- iii. Daily, immediately before and 30 minutes after each Biophotas Celluma treatment

Itching

Itching shall be assessed using an 11-point Visual Analogue Scale (VAS) (0-10-point scale). The Scale will be used at the following timepoints.

Daily, immediately before and 30 minutes after each Biophotas Celluma treatment.

STATISTICAL ANALYSIS PLAN

The primary endpoint measured in the study is length of days to reach either a 0 or 1 on the 11-point scale for erythema, swelling, and crusting, as well as 80-100% overall healing on the treatment arm compared to the control arm. Comparisons of pain, discomfort, and itch ratings will also be made between treatment and control arms by calculating the average scores.

Times to full healing and times to resolution of all side effects will be described by frequency distributions together with mean values and associated 95% confidence limits.

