A comparable study of LED therapy involving 10 patients gave mean (SD) treated healing time of 13.5 (1.1) days and mean (SD) untreated healing time of 26.8 (1.6) days. Mean (SD) of relative reduction in healing time was 50% (2.2%) and the lowest relative reduction was 48%. Assuming similar results for the proposed study, the study size of 25 would virtually guarantee statistically significant reductions in healing time. Based on 95% confidence intervals, the mean treated healing time, mean untreated healing time and mean relative reduction in healing time will be estimated with precisions of 3.1%, 2.3% and 1.7%.

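### Pain, discomfort and itch are compared between a subject's two arms by average scores alone, with no within-subject difference, no interval and no rule on which readings are averaged

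*Combined protocol and SAP*

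**What the plan says.** The hypothesis in Background & Purpose of the Research is that "LED therapy will result in less post treatment pain and in a faster healing time". The same section adds: "A secondary outcome measure will be post-treatment pain on a 10-point scale". No time point or summary measure is attached to either statement. Under Study Design, the control is the subject's other arm and the side is randomized, so the scores come in pairs.

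The Statistical Analysis Plan treats the symptom scores in one sentence: "Comparisons of pain, discomfort, and itch ratings will also be made between treatment and control arms by calculating the average scores". The 95% limits that follow belong to times. They cover how long complete healing takes, and the same sentence says that "times to resolution of all side effects will be described by frequency distributions together with mean values and associated 95% confidence limits". The sample size paragraph concerns healing time only: "the study size of 25 would virtually guarantee statistically significant reductions in healing time".

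Subject assessment lists when pain and discomfort are scored: just after the laser, 30 minutes after the first LED session, then daily before and 30 minutes after each session. The Study Narrative starts itch on day 2. The schedules behind these readings disagree. Research Procedures gives "3 treatments per week for 4 weeks" and says "Day 1, 3, 6 subjects will record daily site symptoms including pain and discomfort and complete a treatment log in a patient diary". Item 11 of the Study Narrative says "Subjects will be instructed to treat the test site daily for 28 days", with daily diaries.

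**The concern.** Two arm averages with no measure of uncertainty do not show whether a pain difference exceeds chance, and the plan does not say that the pairing will be used to obtain one. Nor does it say what happens when a subject has scores for one site only, in which case the two averages would no longer rest on the same subjects and days.

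The choice of readings is also open. Pain after a superficial laser wound may differ between sites early or late, and the documents do not say which is expected. A four-week average and a first-week average of the same diary can give quite different numbers. With no window fixed, one can be chosen after the arms have been compared.

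The pairing also depends on how the diary is filled in. Only the day-0 rating 30 minutes after LED is stated for both sites (Research Procedures; Study Narrative item 10). The later readings are timed to LED sessions that the control arm does not receive.

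**Working it through.** **1. The plan's own precision figures.** Inputs from the SAP: n = 25; healing time mean (SD) 13.5 (1.1) days treated and 26.8 (1.6) days untreated; relative reduction 50% (2.2%). Half-width as a percentage of the mean = 1.96 × SD / √25 / mean.
- Treated: 1.96 × 1.1 / 5 / 13.5 = 3.19% (stated 3.1%)
- Untreated: 1.96 × 1.6 / 5 / 26.8 = 2.34% (stated 2.3%)
- Relative reduction: 1.96 × 2.2 / 5 / 50 = 1.72% (stated 1.7%)

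The stated figures are therefore 95% half-widths at n = 25, the first apparently truncated. The third is an interval for a relative reduction, summarised with its own SD. No such figure is given for pain, discomfort or itch.

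**2. Precision of a symptom-score difference.** The documents give no SD or within-subject correlation (ρ) for these scores, so both are assumed.
- Paired half-width = t(0.975, 24) × SD of differences / √25 = 2.064 / 5 × SD = 0.413 × SD. For SDs of the differences of 1, 2 and 3 points: 0.41, 0.83 and 1.24 points.
- SD of differences = per-site SD × √(2(1 − ρ)). With a per-site SD of 2, the paired half-width is 1.17 (ρ = 0), 0.83 (ρ = 0.5), 0.64 (ρ = 0.7) and 0.52 (ρ = 0.8).
- Ignoring the pairing: t(0.975, 48) × 2 × √(2/25) = 1.14 points.
- For per-site SDs of 1.5 to 2.5: 0.62 to 1.03 paired (ρ = 0.5), against 0.85 to 1.42 unpaired.

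**3. What pooling all readings would do.** This is one possible reading of the SAP sentence. Post-LED here means any reading after the first LED session; the comparison window is week 1. For a constant difference that begins with the first session and ends within week 1, the dilution factor is the number of all readings divided by the number of post-LED readings in week 1.

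| Schedule | All pain readings | Post-LED, week 1 | Factor |
|---|---|---|---|
| Diary days 1, 3, 6, two readings each | 2 + 3×2 = 8 | 1 + 3×2 = 7 | 8/7 = 1.14 |
| Daily, days 0–27 | 2 + 27×2 = 56 | 1 + 6×2 = 13 | 56/13 = 4.3 |
| Three sessions a week, 12 in all, two readings each | 2 + 11×2 = 24 | 1 + 2×2 = 5 | 24/5 = 4.8 |

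Example: take an assumed 2-point difference that lasts through day 3. On the daily schedule it covers 1 + 2×3 = 7 readings, giving 2×7/56 = 0.25 pooled and 2×7/13 = 1.08 in week 1. On diary days 1, 3, 6 it covers 1 + 2 + 2 = 5 readings, giving 2×5/8 = 1.25 pooled.

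The factor depends on duration. On the daily schedule a difference lasting to day 13 gives 2×27/56 = 0.96 against 2, a factor of 2.1. One lasting to day 27 gives 2×55/56 = 1.96 against 2, a factor of 1.02. Dropping only the reading taken before any LED moves 0.250 to 2×7/55 = 0.255, so that reading hardly matters.

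**The case against.** The strongest reply is that the SAP sentence is brief rather than wrong. With complete pairs, the difference between the two arm averages equals the mean within-subject difference, so the planned estimate is sound, and any analyst could add a paired interval from the same data. That stands for the point estimate. It does not supply the interval, the window or a rule for incomplete pairs, none of which is written down.

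A reader might infer that the SAP pools every reading to day 27 and so dilutes an early effect four-fold. The text does not say so. An average across subjects at each listed time point fits the sentence equally well, and then nothing is diluted. If diary days 1, 3 and 6 apply, the factor is only 1.14.

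Nor is a smaller pooled mean the same as lost evidence. If late scores are zero at both sites, late differences add neither signal nor noise; the mean difference and its SD shrink together, and the paired t is almost unchanged. For the same reason, a pooled 0.25 should not be set against the half-widths in step 2, whose SDs are tied to no window.

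A reader might also infer that the control site is not scored in the diary. The planned between-arm comparison implies that it is, and the subject may well rate both sites in one sitting. The gap is that this is not stated beyond day 0.

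**Conclusion.** The point holds as a gap in the analysis of a named secondary outcome. Followed as written, the plan yields average scores by arm with no standard error, no interval for the difference and no treatment of incomplete pairs. The 95% limits elsewhere in the SAP do not fill the gap: it does not say whether pain, discomfort or itch count as side effects, and even if they do, those limits describe times, not scores.

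The gain from pairing rests on assumed values: 0.83 against 1.14 points at SD 2 and ρ = 0.5, and none at ρ = 0. The dilution range of about 1.1 to 4.8 applies only if all readings are pooled and the effect ends in week 1; it overstates the loss of evidence to the extent that it is a change of scale.

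It would go too far to conclude that the pain half of the hypothesis cannot be judged. The plan is underspecified, but the design supports a paired analysis if both sites are scored. The primary healing endpoint is not affected. The change should be made, but it does not put the trial in question.

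**What to change.** - State that both sites are scored at every reading, at the same time.
- For each subject, compute the test-minus-control difference in the mean of post-LED readings over one window fixed before the arms are compared. Week 1 is an example; the choice is the sponsor's. For itch the window cannot start before day 2, its first recorded day.
- Report the mean difference with a paired 95% CI, show the other days the same way as supportive, and say how a subject with readings from one site only is handled.
- Reconcile Research Procedures, the Study Narrative and Subject assessment on diary days and session frequency. No view is taken here on which is right, but a reading rule cannot be written until they agree.
- If the diaries are already complete, fix the window before comparing the arms, limit the comparison to time points scored at both sites, and say so in the report.

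The cost is a few lines in the SAP and one extra diary column per site, with slightly more burden on subjects. A fixed window may miss a later difference, which is why the other days are still shown. With data already collected, some comparisons may have to be dropped.

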- 1. Subjects will return to the clinic on days 2, 4, 6, 9, 13, 20 and 27. * Scheduled follow-up visits may be adjusted 1-2 days based on clinic or patient availability.
- 2. The subject will be questioned generally to ascertain any changes in health or concomitant medication.
- 3. The subject's diary will be reviewed, and the subject will be questioned to ascertain any potential adverse incidents.
- 4. Clinical digital photography of test and control site will be recorded.
- 5. The Investigator will assess both test and control sites using visual analogue scales to include time to heal, percentage healing, edema, erythema, swelling and crusting.
- 6. Subject will assess treatment response using a grading of response.
- 7. The subject will be given a date and time to return to the clinic for the next assessment.

Day 34

- 1. The subject will be questioned generally to ascertain any changes in health or concomitant medication.
- 2. Clinical digital photography of test and control site will be recorded.
- 3. The Investigator will assess both test and control sites using visual analogue scales to include time to heal, percentage healing, edema, erythema, swelling and crusting.
- 4. Subject will assess treatment response using a grading of response.
- 5. The subject will be given a date and time to return to the clinic for the last assessment.

Day 55

- 1. The subject will be questioned generally to ascertain any changes in health or concomitant medication.
- 2. Clinical digital photography of test and control site will be recorded.
- 3. The Investigator will assess both test and control sites using visual analogue scales to include time to heal, percentage healing, edema, erythema, swelling and crusting.
- 4. Subject will assess treatment response using a grading of response. If there are no continuing adverse events and the patient has completed all diaries, they will be allowed to keep the Celluma device, and signed off the study.

Digital photographs will be taken of each ventral arm from antecubital fossa to axilla before laser application, directly after laser application, and at designated assessment visits in clinic. The photos will only include the ventral arm in the frame. If there are tattoos present in the area they will be covered using a black photography cloth or blue medical drape.

Subject will be asked to give consent prior to participating in the study by signing an informed consent form and photography release form.

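### The SAP promises mean times to resolution of all side effects, but symptom scores stop at day 27 with no censoring rule, and discoloration and scarring are scheduled at most once

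*Combined protocol and SAP*

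**What the plan says.** The Statistical Analysis Plan contains two sentences that bear on this point. One reads "Times to full healing and times to resolution of all side effects will be described by frequency distributions together with mean values" and goes on to add 95% confidence limits. The one before it reads "Comparisons of pain, discomfort, and itch ratings will also be made between treatment and control arms by calculating the average scores". Neither says which signs or symptoms count as side effects, what counts as resolved, or what to do with a site that has not resolved at its last rating.

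The schedule in the protocol is as follows.

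- **Pain and discomfort.** These are rated on day 0. Then, under Days 1-27 of the Study Narrative: "Daily, immediately before and 30 minutes after each Biophotas Celluma treatment the subject will record pain and discomfort".
- **Itch.** The same section says "From Day 2-27 subjects will record itching immediately before and 30 minutes after each Biophotas Celluma treatment".
- **After day 27.** The Day 34 and Day 55 steps schedule no pain, discomfort or itch score.
- **Investigator-assessed signs.** At the clinic visits on days 2, 4, 6, 9, 13, 20 and 27, and again on days 34 and 55, the Study Narrative says "The Investigator will assess both test and control sites using visual analogue scales to include time to heal, percentage healing, edema, erythema, swelling and crusting".
- **Discoloration and scarring.** Both are listed under Methods of evaluation. The Day 55 final follow-up in Research Procedures has the list "Time to heal, Percentage healing, edema, erythema, swelling, crusting, discoloration, and scarring". The Day 55 step in the Study Narrative omits both items. Methods of assessment gives no grading scale for either.

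**The concern.** A mean time to resolution needs repeated observation until the event, or a rule for sites where observation ends first. For the symptoms, recording follows the LED course rather than the wound. It ends at day 27, while the plan's sample-size passage expects untreated sites to heal at a mean of 26.8 days and treated sites at 13.5. If symptoms persist in step with the wound, the unobserved resolutions fall almost entirely on the control arm. A simple mean would then be biased in one arm only. For discoloration and scarring, a single late look shows presence or absence on that day and not when a change happened.

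What is at stake is a descriptive secondary summary and the LED-control contrast in side-effect duration. The primary endpoint is not at stake.

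**Working it through.** **1. The plan's own figures.** The inputs are in the last paragraph of the SAP: treated healing time 13.5 (SD 1.1) days, untreated 26.8 (SD 1.6) days, relative reduction 50% (SD 2.2%), n = 25. The relative half-width of a 95% interval is 1.96 × SD / √25 / mean.

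- Treated: 1.96 × 1.1 / 5 / 13.5 = 3.19%
- Untreated: 1.96 × 1.6 / 5 / 26.8 = 2.34%
- Relative reduction: 1.96 × 2.2 / 5 / 50 = 1.72%

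The plan states 3.1%, 2.3% and 1.7%, which match after truncation to one decimal. These figures concern healing time and do not depend on the symptom schedule.

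**2. Promise against schedule.**

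| Outcome | Planned recording | Time to resolution available? |
|---|---|---|
| Edema, erythema, swelling, crusting | Days 2, 4, 6, 9, 13, 20, 27, 34, 55 | Yes, to within the gap between visits (7 days from 27 to 34, 21 days from 34 to 55) |
| Pain, discomfort | Day 0, then around LED sessions to day 27 | Yes if resolved by day 27; otherwise right-censored |
| Itch | Around LED sessions, days 2 to 27 | Same |
| Discoloration, scarring | Day 55 in one list, absent from the other | No; status on one day at most |

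**3. Share of sites censored at day 27.** The documents give no symptom durations, so a range is needed. Assume a normal shape with mean m and, for control sites, the SD of 1.6 that the plan gives for untreated healing. Then P(T > 27) = 1 − Φ((27 − m)/1.6).

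- m = 20: 1 − Φ(4.375), about 0%
- m = 24: 1 − Φ(1.875) = 3%
- m = 26.8, symptoms lasting as long as the wound: 1 − Φ(0.125) = 45%, and 25 × 0.45 is about 11 sites
- m = 30: 1 − Φ(−1.875) = 97%

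For treated sites with symptoms lasting as long as the wound, (27 − 13.5)/1.1 = 12.3, so the share is essentially 0%.

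**4. Effect on a simple mean when m = 26.8.** Here φ(0.125) = 0.396 and Φ(0.125) = 0.550.

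- Unresolved sites dropped: 26.8 − 1.6 × 0.396/0.550 = 25.6 days
- Day 27 carried as the time: 27 − (0.2 × 0.550 + 1.6 × 0.396) = 26.3 days

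Against a treated mean of 13.5, the true difference is 26.8 − 13.5 = 13.3 days. It would read 25.6 − 13.5 = 12.1 days (about 9% too small) or 26.3 − 13.5 = 12.8 days (about 4% too small).

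**5. How firm the symptom window is.** The diary ratings are tied to LED sessions, and the two accounts of those sessions differ. Research Procedures says "Test site will receive a 30-minute treatment of Celluma, 3 treatments per week for 4 weeks" and names days 1, 3 and 6 for symptom recording. The Study Narrative says "Subjects will be instructed to treat the test site daily for 28 days and to complete their treatment log and diaries daily". The two passages must be reconciled. Under the sparser account fewer symptom times are observable than in step 3. After day 0 the text also does not say that the control site is scored separately.

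**The case against.** The strongest reply is about scope. Side effects is undefined. The preceding SAP sentence gives pain, discomfort and itch their own analysis by average score. The only signs with a stated threshold (0 or 1 on the 11-point scale) are erythema, swelling and crusting, and these are followed to day 55. Discoloration and scarring are listed as treatment response and never called side effects. On that narrow reading the promise can be kept, subject to visit spacing. This stands as a possible reading. But the sentence says all and excludes nothing, so the SAP has to state the scope.

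The reply is also right against three stronger inferences that a reader might draw.

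- *That times for pain, discomfort and itch cannot be obtained.* Under the daily diary, any symptom that resolves by day 27 has an observable time. Only later ones are censored.
- *That 45% of control sites lose symptom data.* The 45% is the share of control wounds unhealed after day 27. It measures symptom loss only if symptoms last as long as the wound, which the documents do not say. It is also sensitive to the cut-off, because 26.8 is so close to 27: the same curve gives 23% beyond day 28 and 8% beyond day 29.
- *That discoloration and scarring cannot be recovered.* Both sites are photographed at every assessment, so later grading is possible. It is simply not planned.

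Adverse events are recorded, changes in health are asked about at days 34 and 55, and sign-off depends on there being no continuing adverse event. A persistent symptom need not go unnoticed, but none of this produces a score or a resolution date.

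**Conclusion.** The point holds in a limited form. The SAP promises more than the schedule delivers. The clinic-assessed signs are covered to day 55. Pain, discomfort and itch are covered to day 27, with right-censoring beyond that and no rule for it. No time to resolution of discoloration or scarring can come from the planned grading, and the two Day 55 lists contradict each other however side effects is read.

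The number of censored symptom times is unknown. The range of about 0% to 45% of control sites for mean durations of 20 to 26.8 days (97% at 30 days) rests on an assumed normal shape, an SD borrowed from healing times, and assumed symptom durations. Even at 26.8 days the error in a simple control mean is about 0.5 to 1.2 days. It makes the LED-control difference look smaller, so a reader should not infer that this gap could create a false benefit for LED. The primary endpoint and the precision figures for 25 subjects are not affected. The point is worth acting on because the repair is cheap, not because it threatens the main result.

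**What to change.** 1. **In the SAP**, list the signs and symptoms that count as side effects. Define resolution, for example a score of 0 or 1 as in the primary endpoint. Treat sites unresolved at the last rating as censored, and replace the simple mean with a time-to-event summary, such as Kaplan-Meier estimates with medians and 95% limits.
2. **In the diary and visit schedule**, rate pain, discomfort and itch separately for each site, not tied to an LED session, once daily to day 34 and again at the Day 55 visit (and day 62 if held). A symptom that resolves between days 34 and 55 is then known only to that interval, which the analysis should respect.
3. **Reconcile the Day 55 lists** in Research Procedures and the Study Narrative so that discoloration and scarring are assessed. Then either grade both at each visit from the photographs already planned, on a stated scale, or report them as Day 55 status only and take them out of the time-to-resolution sentence.

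The two accounts of LED session frequency and diary days also need to be reconciled, since the symptom ratings now hang on them.

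The cost is about one more week of once-daily ratings (days 28 to 34), symptom ratings at an existing visit, and, if grading is chosen, a scale for discoloration and scarring and the time to apply it. Diary and grading work rises slightly, and no new visits are needed.
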